9.1.3 Special management orders in conjunction with imatinib monotherapy

- ♦ Myelosuppression can occur at any time during imatinib therapy, but it generally occurs within 2 to 4 weeks. Use of growth factors (G-CSF and GM-CSF) may be initiated with recurrent grade ≥ 3 neutropenia. Dose titration is recommended to keep ANC $> 1.5 \times 10^9/l$. Dose adjustments should be made according to section 9.1.1.
- ♦ In most cases rash is mild, self-limiting and manageable with antihistamines or topical steroids. A short course of oral steroids may be initiated for the management of more severe cases. Prednisone 25 mg is recommended for one week or until rash has resolved.
- ♦ Patients should be monitored closely for peripheral edema and rapid weight gain. The use of diuretics may be initiated for the management of edema. In severe cases imatinib should be withheld and the edema may be controlled with diuretics. Imatinib can be resumed, while maintaining or increasing diuretic therapy.
- ♦ Routine liver function tests should be performed throughout the study. It is also recommended that patients be screened for viral hepatitis at the screening visit. Dose reduction may be warranted and the decision to continue imatinib needs to be made in light of the clinical situation.

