9.1.1 Dose adjustments during imatinib monotherapy

Hematological toxicity

Grade 1 and 2:

No dose adjustments for grade 1 and 2 hematological toxicity will be made.

Grade 3 and 4:

If a patient experiences a grade ≥ 3 neutropenia and/or thrombocytopenia (i.e., ANC $< 1.0 \times 10^9/l$, or a platelet count $< 50 \times 10^9/l$), imatinib must be withheld until the toxicity has resolved to grade ≤ 2 .

ANC takes precedence over WBC in determining the degree of neutropenia. If the hematological toxicity resolves to grade ≤ 2 within 2 weeks, imatinib may be resumed at a dose of 800 mg/day, as appropriate. If the grade ≥ 3 hematological toxicity recurs or persists for longer than two weeks, imatinib must be withheld and reduced to 600 mg/day once toxicity has resolved to grade ≤ 2 . If the grade ≥ 3 hematological toxicity recurs after dose reduction to 600 mg, imatinib must be withheld and may be resumed at 600 mg/day upon recovery to grade ≤ 2 . If the grade ≥ 3 hematological toxicity recurs, imatinib must be withheld and reduced to 400 mg/day once toxicity has resolved to grade ≤ 2 .

If the grade ≥ 3 neutropenia and/or thrombocytopenia recurs after dose reduction to 400 mg/day, imatinib must be withheld and resumed at 400 mg/day upon recovery to grade ≤ 2 . If the grade ≥ 3 hematological toxicity recurs, imatinib must be withheld and reduced to 300 mg/day upon recovery to grade ≤ 2 . If the grade ≥ 3 hematological toxicity recurs after dose reduction to 300 mg/day, imatinib must be withheld and resumed at 300 mg/day upon recovery to grade ≤ 2 . If at any time the hematological toxicity does not resolve to grade ≤ 2 in 28 days, consult with the study coordinator.

No dose reductions will be performed for grade ≥ 3 anemia or lymphopenia. Patients developing anemia may be transfused or prescribed erythropoietin at the discretion of the treating physician.

Non-hematological toxicity

Grade 1:

No dose adjustments for grade 1 non-hematological toxicity will be made.

Grade 2:

If a patient experiences a grade 2 non-hematological toxicity that does not resolve despite

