11.1 Time of clinical evaluations

Arm A:

- ◆ At entry: before start imatinib*
- ◆ ≤ 12 months from entry: at 3, 6 and 12 months after start imatinib
- ◆ > 12 months from entry: every 6 months
- ◆ Follow up: every 6 months

Arm B:

- ◆ At entry: before start imatinib*
- ◆ After cytarabine cycle I: approximately 4 weeks after start cycle I
- ◆ After cytarabine cycle II: approximately 4 weeks after start cycle II

- ◆ Imatinib monotherapy: every 6 months, with the first clinical evaluation at 6 months after entry
- ◆ Follow up: every 6 months

* For patients treated with imatinib prior to entry in the study baseline evaluations are those performed before start imatinib, if available. If unavailable, baseline evaluations should be performed at entry.

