11.2.10 Additional investigations during cytarabine treatment

- ◆ Platelet count, WBC and differential at least 2-3 times weekly
- ◆ BUN, creatinine, sodium, potassium, calcium, glucose daily during chemotherapy, and thereafter at least twice weekly
- ◆ ALAT, ASAT, alkaline phosphatase, γ -GT, bilirubin and LDH at least weekly
- ◆ Routine urine analysis weekly
- ◆ X-Thorax once during the first week, thereafter as clinically indicated

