17.2.2 Toxicity analysis

The analysis of treatment toxicity will be done primarily by tabulation of the incidence of side effects and infections with CTCAE grade 2 or more (see appendix D) by treatment arm (and cycle cytarabine, arm B only).

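### The required blood-count schedule cannot support the protocol's own hematological dose rules, and laboratory toxicity may be detected unequally between the arms

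*Protocol*

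**What the plan says.** **Onset.** Protocol section 9.1.3, on imatinib monotherapy: "Myelosuppression can occur at any time during imatinib therapy, but it generally occurs within 2 to 4 weeks".

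**Dose rules.** Under section 9.1.1, once neutrophils fall below 1.0 × 10⁹/l or platelets below 50 × 10⁹/l, "imatinib must be withheld until the toxicity has resolved to grade" 2 or lower. What follows depends on how long recovery takes. One branch reads "If the hematological toxicity resolves to grade ≤ 2 within 2 weeks, imatinib may be resumed" at 800 mg/day. The other covers grade 3 or higher toxicity that "recurs or persists for longer than two weeks, imatinib must be withheld and reduced to 600 mg/day" after recovery. If toxicity has not resolved to grade 2 or lower, the instruction is "in 28 days, consult with the study coordinator".

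**Required counts, arm A.** Section 11.1 sets the first-year evaluations "at 3, 6 and 12 months after start imatinib". The section 11.2 table lists hematology at entry and then at month 3; the on-treatment columns in between are labelled arm B only.

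**Required counts, arm B.** Under section 9.2, cytarabine cycle I starts preferably within 14 days of starting imatinib and at the latest at 4 weeks. No count is listed for that interval. During cytarabine treatment section 11.2.10 requires "Platelet count, WBC and differential at least 2-3 times weekly", with liver tests at least weekly. Section 11.1 adds an evaluation about 4 weeks after the start of each cycle.

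**Analysis.** Section 17.2.2 plans mainly a "tabulation of the incidence of side effects and infections with CTCAE grade 2 or more", by treatment arm and, in arm B, by cytarabine cycle. Toxicity is a secondary endpoint (section 14).

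**The concern.** The dose rules and the investigations table do not fit together. The rules need serial counts a few weeks apart, starting in the period when the protocol itself expects myelosuppression. A site that follows the arm A table exactly has no count in that period.

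Two things are at stake. The first is safety: an early grade 3-4 cytopenia on 800 mg imatinib alone may not be seen in time for the protocol's own rules to be applied. Arm B has a shorter gap of the same kind before cycle I. The second is the toxicity comparison. An asymptomatic laboratory event can be recorded only if a sample was taken, and sampling is dense in arm B around the cycles and sparse in arm A. Part of any excess of laboratory toxicity in arm B could then reflect how often blood was drawn.

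**Working it through.** The plan gives no figure of its own on this point, and the sample size of 330 does not depend on it. The check sets the stated time windows against the required count times.

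**1. Could the month-3 count show an early episode in arm A?** Inputs: onset at week 2 to 4 (section 9.1.3), the 2-week and 28-day limits (section 9.1.1), first on-treatment count at month 3 (sections 11.1 and 11.2). Month 3 = 365.25 / 4 / 7 = 13.0 weeks.

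| Onset (week) | Duration (weeks) | Ends (week) | Gap to month 3 (weeks) |
|---|---|---|---|
| 2 | 2 | 4 | 13.0 − 4 = 9.0 |
| 4 | 2 | 6 | 13.0 − 6 = 7.0 |
| 2 | 4 | 6 | 13.0 − 6 = 7.0 |
| 4 | 4 | 8 | 13.0 − 8 = 5.0 |

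To be visible at month 3, an episode would have to last 13.0 − 4 = 9.0 to 13.0 − 2 = 11.0 weeks. The durations in the table are assumptions borrowed from the rule limits; the protocol gives no typical duration.

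**2. Can the rules be operated on the required counts?** This needs no assumption about duration. Separating recovery within 2 weeks from persistence beyond 2 weeks needs counts no more than about 2 weeks apart. The 28-day rule needs one by day 28. The first required interval in arm A is about 91 days, and the later ones are 3 and then 6 months. All exceed both limits.

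**3. Arm B before cycle I.** The interval without a required count is preferably up to 14 days, at most 28. On the preferred schedule, counts begin by about the opening of the 2-4 week window; at the outer limit the whole window is uncovered.

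**4. Required counts during cytarabine treatment.** Section 11.2.10 gives no end date, so the total is a range:
- the two 7-day courses only: 2 weeks × 2-3 per week = 4-6;
- about 4 weeks per cycle: 2 × 4 weeks × 2-3 per week = 16-24.

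The chemistry line in the same section continues after chemotherapy, which points to the longer reading but does not settle it. Arm A has one required on-treatment count by month 3.

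**5. What unequal detection could do (illustration only).** Assumptions not in the protocol: the same true incidence p in both arms, to isolate detection; full detection in arm B; a fraction d detected in arm A. Arm size is 330 / 2 = 165. The spurious excess in arm B is p − pd = p(1 − d). The chance of a nominal two-sided P < 0.05 is about Φ[(Δ − 1.96·s₀)/s₁], where Δ = p − pd, s₀ is the pooled and s₁ the unpooled standard error. For p = 0.30 and d = 0.75: Δ = 0.075, s₀ = √(2 × 0.2625 × 0.7375 / 165) = 0.0484, s₁ = √((0.225 × 0.775 + 0.30 × 0.70) / 165) = 0.0483, so Φ(−0.41) = 34%.

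| p | d = 0.90 | d = 0.75 | d = 0.50 |
|---|---|---|---|
| 0.20 | 2 points, 7% | 5 points, 22% | 10 points, 72% |
| 0.30 | 3 points, 9% | 7.5 points, 34% | 15 points, 91% |
| 0.40 | 4 points, 11% | 10 points, 48% | 20 points, 98% |

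At d = 1 there is no distortion. The protocol gives no value for d, and section 17.2.2 plans a tabulation, not a test. The table shows sensitivity and is not a forecast.

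**The case against.** The strongest reply is that the table sets a minimum and the dose rules already presuppose more frequent counts: nobody can withhold imatinib at a neutrophil threshold without measuring neutrophils. Section 13 counts an abnormal laboratory finding as an adverse event, and section 13.2 makes every grade 2 or higher event in the treatment period reportable, whether or not a visit was scheduled. Unscheduled counts are not forbidden. Closer monitoring around intravenous chemotherapy is also normal.

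This defeats several stronger readings that a reader might infer:

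- *That early toxicity in arm A is missed.* It may be. Symptomatic or serious cytopenia would surface as an adverse event, and clinicians may take extra counts.
- *That a month-3 count has practically no chance of showing an early episode.* That assumes a 14-day episode, but the 2-week window describes recovery with imatinib withheld. An undetected cytopenia would not lead to withholding and could last longer.
- *That the arm comparison as a whole is biased.* The primary endpoint is major molecular response at 12 months, with PCR scheduled in both arms, so this detection difference does not touch it. The sequential safety monitoring in section 17.4 uses reported SAEs and deaths, not scheduled counts.
- *That re-escalation under section 9.1.2 also cannot be applied.* Its one month is a minimum, which a later visit can satisfy.
- *That dense counts in arm B distort imatinib dose intensity.* Section 9.2.1 continues imatinib through cytopenia after combination therapy and interrupts it only for grade 4 hematological toxicity lasting more than 4 weeks. Most of those counts would not trigger a change, and the dose rules differ by arm by design.

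What remains is that a duty to report is not a duty to sample. The synopsis has adverse events documented if observed, mentioned on open questioning or spontaneously reported. If sites add counts, their frequency is left to each site in arm A and fixed in arm B, so detection can still differ. The reference in section 9.1.3 to routine liver tests throughout the study gives no times and does not cover blood counts.

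**Conclusion.** The point holds as an inconsistency within the protocol. The required schedule cannot support the hematological dose rules of section 9.1.1: arm A has about 13 weeks without a required on-treatment count, against limits of 2 weeks and 28 days, and arm B has up to 4 weeks without one before cycle I. This follows from the stated times alone.

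That laboratory toxicity is detected less completely in arm A is a reasonable risk, not an established fact. The likely direction is that arm B looks relatively more myelosuppressive than it is. The size depends on how many unscheduled counts arm A sites take, which the protocol does not say; it could be nil. The risk is confined to the laboratory part of the by-arm toxicity tabulation. The point should be corrected, but it does not threaten the primary result.

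**What to change.** **Schedule.** Reconcile the investigations table in sections 11.1 and 11.2 with sections 9.1.1 and 9.1.3, in both arms and including arm B before cycle I. The count times are for the clinical team to set. State when the arm B counts in section 11.2.10 end. Record the resulting counts on the CRF.

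**Analysis.** In section 17.2.2:
- keep the full by-arm tabulation, including the arm B cycles;
- add a supplementary by-arm table of laboratory toxicity at the time points required in both arms;
- state that count frequency differed by arm.

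The supplementary table must not replace the full one. Restricting the comparison to common time points would leave out the low counts after cytarabine and hide a real toxicity of arm B.

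**Cost.** An amendment to the investigations table and CRF, a few sentences in section 17.2.2, and more routine blood results to collect and enter. No new kind of procedure is needed, since the dose rules already presuppose counts.

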9.2 Imatinib and cytarabine combination therapy (arm B)

Following registration and randomization, preceding therapy with hydroxyurea or imatinib is stopped and imatinib is started at a total dose of 800 mg daily, preferably 2 x 400 mg. The first cycle of i.v. cytarabine is started as soon as possible, preferably within 14 days from the start of imatinib, and at the latest 4 weeks from the start of imatinib. Dose adaptations are outlined in section 9.2.1. During combination therapy, patients will receive imatinib at a total dose of 800 mg, preferably 400 mg twice daily, continuously. Cytarabine is added as a 7 day course of i.v. chemotherapy. Cytarabine is given at a dose of $200 \text{ mg/m}^2/\text{day}$ in 500 ml NaCl 0.65% (or 0.9%) as 1-2 hours infusion, once daily. The second cycle of cytarabine will be started if there is evidence of hematopoietic recovery (platelets $> 100 \times 10^9/l$ and WBC $> 2.0 \times 10^9/l$), when evaluation procedures after cycle I have been performed and when all toxicities have resolved to grade ≤ 1 . Cycle II should be started within 8 weeks from the start of cycle I. If start of cycle II within 8 weeks from start of cycle I is not possible, patients should continue with imatinib monotherapy.

Combination therapy may be administered on an outpatient basis. However, it is advocated to admit patients clinically in case of grade 4 hematological toxicity (e.g. ANC < $0.5 \times 10^9/l$). Alternatively patients may be followed up frequently (3 times per week) in the outpatient clinic, with immediate clinical admittance in case of fever.

9.2.1 Dose adjustments during imatinib and cytarabine combination therapy

Dose adjustments outlined below should be adhered to from the start of cytarabine until hematological recovery following the last combination therapy cycle given. Hereafter dose adjustments should be made according to 9.1.1.

Hematological toxicity

Imatinib is continued during the phase of cytopenia following combination therapy. However, grade 4 hematological toxicity, which persists for more than 4 weeks, should be followed by interruption of imatinib until resolution of hematological toxicity to grade ≤ 2 . Thereafter imatinib should be resumed at the targeted dose and subsequent adaptations of dose should be made according to 9.1.1.

Non-hematological Toxicity

No dose modifications will be made for cytarabine.

No dose modifications of imatinib will be made for grade 1, 2 and 3 toxicity (except for grade 3 liver toxicity).

If a patient experiences any of the following toxicities, imatinib must be withheld until toxicity has resolved to grade < 2 and then be resumed at the targeted dose:

- ♦ grade 4 stomatitis which persists for longer than 1 week;
- ♦ grade 3 or 4 liver toxicity;
- ♦ any other grade 4 toxicity (except hematological toxicity, nausea and vomiting).

9.2.2 Special management orders in conjunction with combination therapy

- ♦ Infections should be controlled before start of chemotherapy.
- ♦ Anti-bacterial prophylaxis and anti-fungal prophylaxis should be given, for example oral ciprofloxacin 500 mg (2 x) and oral fluconazole tablets 200 mg (1 x), or according to local protocols, from the start of neutropenia.
- ♦ Patients experiencing grade 4 neutropenia (ANC < $0.5 \times 10^9/l$) for longer than 1 week may receive granulocyte colony-stimulating factor (G-CSF) until neutropenia has resolved (ANC > $1.0 \times 10^9/l$). G-CSF should be given at a dose of 5 $\mu\text{g}/\text{kg}$ s.c. once daily.
- ♦ After cytarabine therapy 200 $\text{mg}/\text{m}^2/\text{day}$, special attention should be given to prevent bacteremias by α -hemolytic Streptococci, for example, by oral azithromycin.
- ♦ Cytarabine 200 $\text{mg}/\text{m}^2/\text{day}$ should be discontinued in case of nystagmus or cerebellar symptoms. If those symptoms resolve within 24 hours, cytarabine may be resumed. After

interruption of the cycle, it should not be prolonged after day 7.

9.3 Imatinib monotherapy following combination therapy (arm B)

Following full hematological recovery after the second cycle of i.v. cytarabine and when evaluation procedures have been completed, monotherapy therapy is started. Patients will continue with imatinib at a dose of 800 mg until progression of disease or intolerance of treatment, whichever occurs first (see section 10). Dose adaptations during imatinib monotherapy are outlined in section 9.1.1.

9.4 Concomitant medication

- ◆ In general, concomitant medications and therapies deemed necessary for the supportive care and safety of the patient are allowed.
- ◆ The concomitant administration of investigational drugs is NOT allowed. However, the administration of any other anticancer agents including chemotherapy and biologic agents is NOT permitted.
- ◆ Because of the possible risk of either reduced activity or enhanced toxicity of the concomitant medication and/or imatinib, drugs known to interact with the same CYP450 isoenzymes (CYP2D6 and CYP3A4) as imatinib should be used with caution. Patients using concomitant medications known to be metabolized by these cytochrome P450 enzymes will not be excluded from the study. However, the patients must be carefully monitored for potentiation of toxicity due to individual concomitant medication. Consideration should be given to using alternative agents with less potential for interaction with imatinib.
- ◆ Special care has to be given to the concomitant use of acetaminophen/paracetamol with imatinib. Patients should be counseled to limit the use of over-the-counter medications that contain acetaminophen/paracetamol.
- ◆ Concomitant use of levothyroxine should be carefully monitored and the cumulative dose of levothyroxine should be doubled at start of imatinib treatment.
- ◆ In general, the use of warfarin is discouraged on this protocol. Since warfarin is metabolized through the CYP450 system, patients on therapy with warfarin should have their INR closely monitored. For example, monitoring is suggested every two days during the first two weeks of simultaneous treatment with imatinib, twice per week for the following two weeks, and every 2 weeks until discontinuation of either imatinib or warfarin. As an alternative, therapeutic anticoagulation may be accomplished using low-molecular weight heparin or heparin. Mini-dose warfarin (e.g. 1 mg q.d.) is permitted for prophylaxis of central venous catheter thrombosis, at the discretion of the treating physician.
- ◆ Patients on anticonvulsants should have regular monitoring of plasma concentration of these agents. The routine use of systemic corticosteroid therapy is permitted. Growth factors may be initiated with recurrent grade 3 neutropenia. Prophylactic anti-emetics may be allowed if the patient has experienced grade > 1 nausea or vomiting.

- ◆ Prophylactic use of loperamide (with suggested dosing as start: 4 mg p.o. x 1, than 2 mg p.o. after each loose stool, max 16 mg/day) may be initiated for patients experiencing grade ≥ 2 diarrhea, before dose interruption.

10 End of protocol treatment

Reasons for going off protocol treatment are:

1. Progression*
2. Excessive toxicity (including toxic death) / intolerance of treatment
3. Intercurrent death
4. No compliance of the patient (especially refusal to continue treatment)
5. Major protocol violation

* The following events are considered progression:

- ◆ progression to accelerated phase (see appendix A);
- ◆ progression to blastic crisis (see appendix A);
- ◆ progression without prior complete hematological response (see appendix C);
- ◆ progression with prior complete hematological response (see appendix C);
- ◆ progression from major cytogenetic response (see appendix C);
- ◆ clonal evolution (see appendix C).

11 Required clinical evaluations

Aim of the clinical evaluation at entry is to know in which stage of disease the patients are. Aim of the clinical evaluation during treatment and follow up is to determine toxicities and response. Evaluation of response is described in section 11.3 and appendix C. The Sokal score will be determined at the HOVON Data Center based on data determined at diagnosis (see appendix B) and will be used for stratification prior to randomization (see section 16).

11.1 Time of clinical evaluations

Arm A:

- ◆ At entry: before start imatinib*
- ◆ ≤ 12 months from entry: at 3, 6 and 12 months after start imatinib
- ◆ > 12 months from entry: every 6 months
- ◆ Follow up: every 6 months

Arm B:

- ◆ At entry: before start imatinib*
- ◆ After cytarabine cycle I: approximately 4 weeks after start cycle I
- ◆ After cytarabine cycle II: approximately 4 weeks after start cycle II

- ◆ Imatinib monotherapy: every 6 months, with the first clinical evaluation at 6 months after entry
- ◆ Follow up: every 6 months

* For patients treated with imatinib prior to entry in the study baseline evaluations are those performed before start imatinib, if available. If unavailable, baseline evaluations should be performed at entry.

11.2 Required investigations

	at entry ¹	during cycle I and II (arm B)	after cycle I (arm B) ²	month 3 (arm A) after cycle II (arm B)	month 6	month 12	month 18	months 24, 36, 48, etc.	months 30, 42, 54, etc.
Medical history	X		X	X	X	X	X	X	X
Physical examination	X		X	X	X	X	X	X	X
Hematology	PB		PB	PB	PB	PB	PB	PB	PB
Blood chemistry	PB		PB	PB	PB	PB	PB	PB	PB
Bone marrow									
Bone marrow biopsy	BMB								
Bone marrow aspirate	BMA			BMA ²	BMA	BMA		BMA	
Storage for future studies	BMA				BMA	BMA ³			
Cytogenetic analysis	BMA			BMA ²	BMA	BMA		BMA	
Molecular analysis	PB + BMA		PB	PB + BMA	PB + BMA	PB + BMA	PB	PB + BMA	PB
Specific investigations									
Ultrasonogram spleen/liver	X		o.i.	o.i.	o.i.	o.i.	o.i.	o.i.	o.i.
X-thorax	X		o.i.	o.i.	o.i.				
ECG	X								
Additional investigations	X	X ⁴							

o.i. On indication

PB Peripheral blood sample

BMB Bone marrow biopsy

BMA Bone marrow aspirate

¹ For patients treated with imatinib prior to entry in the study baseline evaluations are those performed before start imatinib, if available. If unavailable, baseline evaluations should be performed at entry.

² If a patient in arm B only receives one cytarabine cycle, evaluations scheduled after cycle II should be performed after cycle I.

³ Hereafter also at progression.

⁴ See 11.2.10.

